2.0 Objectives*

2.1 *Describe the purpose, specific aims, or objectives of this research.*

Aim 1: To determine the feasibility and acceptability of the MMPH in community-dwelling URM adults with PH as a symptom self-management tool.

Aim 1a: Feasibility will be assessed by 1) frequency of home practice (> 2/week) and 2) retention rate (>70% of participants remaining at study completion).

Aim 1b: Acceptability will be determined by 1) participants' evaluation of the MMPH program (composite mean System Usability Scale score > 5, scale 1-7), 2) session completion rate (at least 6 of 8 [75% attendance] by the participants retained at the study end), and 3) qualitative thematic analysis of participants.

Aim 2: To determine the clinical impacts of an MMPH program in PH-symptom, anxiety, and depression reduction among community-dwelling URM adults with PH for symptom management.

2.2 *State the hypotheses to be tested, if applicable.*

NOTE: A hypothesis is a specific, testable prediction about what you expect to happen in your study that corresponds with your above listed objectives.

Hypothesis 1: MMPH will meet feasibility and acceptability targets for URM adults with PH

Hypothesis 2: Participants will report reductions in symptom severity of pain, anxiety, dyspnea, and fatigue at the end of the MMPH modules (short-term impacts). Participants will report decreases in the prevalence and intensity of PH-related symptoms, depression, and improved quality of life at the end of the MMPH program (long-term impacts).

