5.0 Study Design*

5.1 *Describe and explain the study design (e.g. case-control, cross-sectional, ethnographic, experimental, interventional, longitudinal, observational).*

This study will engage community-dwelling URM adults with PH living in the United States. We will use a two-group comparative study design where waitlisted participants will serve as controls. Considering a 20% attrition rate in a behavioral health intervention study, we aim to enroll a total of 20, with at least 16 participants to address study aims (8-10 in each Group).³⁴ As a pilot study, power analysis is not necessary. Statistical analysis will include descriptive statistics, mixed-effect modeling for repeated measures, and within-group and between-groups comparisons using t-tests or Wilcoxon signed-rank test as appropriate and Cohen's d effect size calculation. Multi-time data collection will be done via daily mobile-APP use.

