11.0 Recruitment Methods

N/A: This is a records review only, and subjects will not be recruited. NOTE: If you select this option, please make sure that all records review procedures and inclusion/exclusion screening are adequately described in other sections.

11.1 Describe when, where, and how potential subjects will be recruited.

NOTE: Recruitment refers to how you are identifying potential participants and introducing them to the study. Include specific methods you will use (e.g. searching charts for specific ICD code numbers, Research Participant Groups, posted advertisements, etc.).

There are two ways we will make the study known to potential eligible participants (1) They may hear about the study from their PH doctors during routine clinic visits (2) They may see study flyers in recruiting partners' offices or clinics during their routine care.

Even though we originally proposed that PH doctors send out emails inviting their patients to contact us for potential enrollment, none of the doctors used the letter. They chose to tell their patients about the study verbally, and we only got one referral from RRH. That was the recruitment process we did. As I previously indicated, we are no longer enrolling and will not use it. We only want to complete the study.

Electronic recruitment will include direct email sent using the University at Buffalo's Clinical and Translational Science Institute's (CTSI) Buffalo Research Registry and social media (Facebook). The registry includes names of individuals who have expressed interest in participating in research studies. Facebook-based recruitment will consist of advertisements for the study.

Flyers will be distributed to our referring partners and will be recruited by PH physician referral, self-referral, the use of Buffalo Research Registry, CTSA Hub advertisement, Social Media posts (Facebook), and Research Match. Flyers will be placed by the Research Coordinator at their locations (our referring partners at URMC and RRH). These flyers will be made available in waiting rooms as well as in healthcare professionals' offices.

In both recruitment methods, interested participants will contact the study team directly to initiate the screening as described in section 10.1. None of the referring partners will participate in any screening activities, only referrals.

11.2 Describe how you will protect the privacy interests of prospective subjects during the recruitment process.

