19.0 Data Management and Analysis*

19.1 Describe the data analysis plan, including any statistical procedures. This section applies to both quantitative and qualitative analysis.

As a pilot study, power analysis is not necessary. Statistical analysis will include descriptive statistics, mixed-effect modeling for repeated measures, and within-group and between-groups comparisons using t-tests or Wilcoxon signed-rank test as appropriate and Cohen's d effect size calculation. Multi-time data collection will be done via daily mobile-APP use.

We will follow the standard procedure in quantitative data analysis that includes general data inspection to verify the accuracy, completeness, and normality of the dataset using the SPSS23 program. We will compare clinical outcomes within-group (pre-post) as well as between groups in the post-intervention period. We will follow the recommendation of inappropriate statistical analysis and interpretation specific to each survey. For continuous variables, we will use a paired student t-test, independent t-test analytical approaches. For categorical variables and non-normally distributed variables, we will use non-parametric statistical methods (X2). Frequency distributions will be produced for all variables, and demographic information will be used to describe the sample. The impact of the M-App use on outcome variables will be analyzed using paired t-test and repeated measure ANOVA.

Qualitative data (focused-group interview data) will be analyzed using the standard qualitative thematic analysis procedure. We will transcribe the audio-recorded data and upload it into NViVo data management system. We will adhere to the thematic analysis method, described as follows:

1. A researcher will read and re-read the entire text to get a general sense of the participants' whole experience of being a student during the COVID-19 pandemic. While reading through the transcript, the researcher will take initial notes and perform a general review to get familiar with the data before analyzing the data.
2. The researcher will descriptively open code by dividing the significant text segments into 'meaningful units', keeping the participants' own words. The researcher will re-read all the codes again to eliminate redundancies.

The comparative discussion of these codes with other research team members to achieve a consensus will provide a validation step.

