22.0 Withdrawal of Subjects*

N/A: This study is not enrolling subjects. This section does not apply.

22.1 Describe anticipated circumstances under which subjects may be withdrawn from the research without their consent.

Participants may be withdrawn from the research without their consent if the PI or research team member discovers a participant is in severe psychological distress or is admitted into the hospital for a psychiatric condition.

22.2 Describe any procedures for orderly termination.

NOTE: Examples may include return of study drug, exit interview with clinician. Include whether additional follow up is recommended for safety reasons for physical or emotional health.

NOT APPLICABLE

22.3 Describe procedures that will be followed when subjects withdraw from the research, including retention of already collected data, and partial withdrawal from procedures with continued data collection, as applicable.

We will attempt to use all the available data obtained from all participants (intention to treat). Pre and post comparison of the experimental Group will be conducted as aggregate means using all available data collected.

When participants decide to leave the study, we will ask them if they would allow us to use the data we have collected before their decision to withdraw. If the subjects agree to use the data, the collected data will be handled and analyzed the same as research data. If the participants do not allow the use of the data, we will make every attempt to destroy the data.

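### The Aim 2 group effect is undefined and no baseline adjustment is stated: the only between-group comparison in 19.1 with a time point is post-intervention

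*Combined protocol and SAP*

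**What the plan says.** Section 5.1 sets up two groups, with waitlisted participants as controls. It enrols 20 so that at least 16 remain, 8-10 per group. Its analysis list includes "mixed-effect modeling for repeated measures", and 19.1 repeats the list. Neither place gives the model an outcome, time points, fixed effects or a contrast. The same list has "within-group and between-groups comparisons using t-tests or Wilcoxon signed-rank test as appropriate", with no time point.

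The second paragraph of 19.1 is more definite: "We will compare clinical outcomes within-group (pre-post) as well as between groups in the post-intervention period". It continues: "For continuous variables, we will use a paired student t-test, independent t-test analytical approaches". Repeated-measures ANOVA appears only for the impact of app use, again without covariates.

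Table 1 (12.1) schedules PAHSS, EmPHasis-10, PHQ-9 and CAMS-R in the w0-w1, w3-w4 and w7-w8 columns. Its columns follow the MMPH sessions, and no waitlist schedule is given. Section 3.1 names PAHSS and EmPHasis-10 as the endpoints. Hypothesis 2 is worded within participants: "Participants will report decreases in the prevalence and intensity of PH-related symptoms, depression, and improved quality of life".

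No section names baseline as a covariate, a between-group test of change, or a group-by-time contrast. No section says how participants are assigned to MMPH or waitlist.

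Section 22.3 says of drop-outs: "Pre and post comparison of the experimental Group will be conducted as aggregate means using all available data collected". For those who withdraw it adds: "If the participants do not allow the use of the data, we will make every attempt to destroy the data".

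**The concern.** A waitlist control is there to show what would have happened without the programme. With 8-10 per group, the two groups can easily start at different levels, and a comparison of week-8 scores alone carries part of that difference into the estimated effect. The scores needed to correct for this are scheduled, at least for MMPH participants, but no planned analysis is said to use them. The plan also leaves several group analyses open (a post-only t-test, undated between-group tests, an unspecified mixed model) without saying which one gives the Aim 2 result. The estimate and its Cohen's d could therefore be chosen after the data are seen.

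The second, smaller matter is pre/post change. A paired t-test uses only people with both scores. Aggregate means on all available data set every baseline against the post scores of those who stayed. The two agree only if nobody leaves usable baseline data without a post score, and the protocol itself expects 20% (5.1) or 15% (7.3) attrition.

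**Working it through.** **The plan's own figure.** 16/(1 - 0.20) = 20, so the enrolment in 5.1 reproduces. With the 15% in 7.3, 16/0.85 = 18.8, or 19, which 20 covers. The plan states no alpha, power, effect size, SD or correlation.

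**Assumptions.** Scores are in SD units with equal SD at baseline and week 8, and higher means worse. The baseline-to-week-8 correlation r is 0.3, 0.5 or 0.7. Intervals are two-sided 95%.

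**1. Random allocation, n = 8 per group.**
- The SD of the chance baseline gap is sqrt(2/8) = 0.500. P(|gap| > 0.5) = 2 x (1 - Phi(0.5/0.500)) = 0.317. At n = 10 the SD is sqrt(2/10) = 0.447 and the probability is 0.264.
- A gap of 0.5 SD moves the post-only estimate by r x 0.5 = 0.15 / 0.25 / 0.35 SD.
- Post-only half-width: t(14) x sqrt(2/8) = 2.145 x 0.500 = 1.07 SD.
- ANCOVA: SE = sqrt((1 - r^2) x (2/8) x (1 + 1/12)) = 0.496 / 0.451 / 0.372. Multiplying by t(13) = 2.160 gives 1.07 / 0.97 / 0.80 SD.
- At r = 0.7 the interval is 1 - 0.80/1.07 = 25% narrower. At r = 0.3 nothing is gained.
- In simulation (40,000 trials per r), type I error was 4.8-5.1% for both methods. The post-only test is therefore valid, but it can be less precise.

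**2. Non-random allocation, baseline gap G = 0.5 SD, no true effect.** Error in SD at r = 0.3 / 0.5 / 0.7:

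| Situation | Post-only | ANCOVA | Change score |
|---|---|---|---|
| (a) Both groups follow the same baseline-to-week-8 line | rG = 0.15 / 0.25 / 0.35 | 0 | -(1-r)G = -0.35 / -0.25 / -0.15 |
| (b) The gap is stable over time | G = 0.50 | (1-r)G = 0.35 / 0.25 / 0.15 | 0 |

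ANCOVA is closer to zero than post-only in both situations. Neither ANCOVA nor the change score is best in both.

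**3. Pre/post change in one group, attrition p = 0.20, no true change.** Let g be the baseline gap between leavers and stayers.
- *Dropout depends on the observed baseline* (g = 0.5-1.0, r = 0.5-0.7). Aggregate means show a false improvement of r x p x g, from 0.5 x 0.2 x 0.5 = 0.05 to 0.7 x 0.2 x 1.0 = 0.14 SD. Paired completers show a false worsening of (1-r) x p x g, from 0.3 x 0.2 x 0.5 = 0.03 to 0.5 x 0.2 x 1.0 = 0.10 SD. A mixed model that keeps every baseline is off by 0.00.
- *Dropout depends on stable underlying severity* (g about 0.4-0.75 at r = 0.5 and 0.45-0.9 at r = 0.7). Aggregate means show a false improvement of p x g, from 0.2 x 0.4 = 0.08 to 0.2 x 0.9 = 0.18 SD. Paired completers are off by 0.00. The mixed model shows a false improvement of about (1-r) x p x g, from 0.3 x 0.2 x 0.45 = 0.03 to 0.5 x 0.2 x 0.75 = 0.08 SD.
- *Scale for comparison.* The SE of paired change at n = 8 is sqrt(2(1-r)/8) = 0.35 SD at r = 0.5 and 0.27 SD at r = 0.7.

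**The case against.** The best reply is that the plan already names a suitable tool. A mixed model with baseline as the first occasion and a group-by-time contrast would account for baseline and use incomplete records. A reader might infer that the plan excludes baseline adjustment. The documents do not support that, because the model's terms are unstated and it could adjust. What stands is that 5.1 and 19.1 do not say so and do not make the model the group analysis.

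A reader might also infer that the post-only test is wrong, or that allocation is non-random. Neither follows. The test is valid under random allocation, and the documents are silent on allocation.

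This is a pilot without a power claim, and Hypothesis 2 is within-participant. That makes the group contrast a matter of estimation, but the planned between-group tests and Cohen's d still need one defined contrast.

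On 22.3, the aggregate-means sentence names no test and may be meant as a descriptive summary. Participants who refuse use of their data leave no baseline behind, which shrinks the mismatch. It is also tempting to say that aggregate means and paired completers always err in opposite directions when people who start worse leave. That holds only if dropout depends on the observed baseline. If it depends on stable severity, the paired estimate is not biased at all. This part is a consistency point.

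**Conclusion.** The main point holds as a fault of specification: the Aim 2 group effect is not defined, and the one dated group comparison makes no stated use of baseline. With randomised groups of 8, the cost is a 32% chance of a baseline gap above 0.5 SD, and an interval that adjustment would narrow from 1.07 to 0.97 or 0.80 SD at r = 0.5 or 0.7, with no gain at r = 0.3. If groups were not randomised, a 0.5 SD baseline gap puts 0.15-0.50 SD of error into the post-only contrast. Adjustment reduces this, but in the stable-gap case leaves 0.15-0.35 SD. All correlations and gaps are assumed, since the documents give none.

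The 22.3 mismatch is real but minor. At 20% attrition with worse starters leaving, aggregate means show a false improvement of about 0.05-0.18 SD under either dropout mechanism, which is small beside an SE of 0.27-0.35 SD. Neither alternative is unbiased under every mechanism, so the only robust conclusion is to remove the aggregate-means contrast.

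**What to change.** In 19.1, state that the Aim 2 group effect for each scale is the week-8 difference from ANCOVA adjusted for the baseline value of the same scale, with a 95% CI. Make this conditional on the waitlist group having completed that scale at baseline and week 8. If it did not, say so and report the group comparison as descriptive. State how participants were allocated. If not randomly, say that adjustment reduces but may not remove confounding, and add the change-score contrast as a sensitivity analysis. Write this before outcomes are compared by group.

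In 22.3, replace the aggregate-means sentence with within-person change: the paired analysis, with a mixed model using all available visits reported beside it. Note that each can be biased under some dropout mechanisms, and make 19.1 agree.

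The cost is wording, plus one degree of freedom in the ANCOVA, with no real gain if r is about 0.3. The limit is the data. Section 11.1 says "we are no longer enrolling and will not use it", so waitlist scores that were not collected may no longer be obtainable.

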Table 1 outlines the detail and sequence of study intervention. Enrolled participants will receive 60-min-weekly intervention for 8 weeks period; 2 of which will include video conference practice and the other 6 will include audio-video recording of the sessions. During the study period, they will complete self-guided meditation using M-App for 20 min/day.

12.2 Describe what data will be collected.

NOTE: For studies with multiple data collection points or long-term follow up, consider the addition of a schedule or table in your response.

Please refer to Table 1 regarding data that will be collected: symptom presence and severity, health-related quality of life, depressive symptoms, mindfulness score, clinical and demographic data.

12.3 List any instruments or measurement tools used to collect data (e.g. questionnaire, interview guide, validated instrument, data collection form).

Include copies of these documents with your submission.

Response: The following questionnaires will be included in this study:

- Cognitive and Affective Mindfulness Scale-Revised (CAMS-R)
- The Patient Health Questionnaire-9 (PHQ-9)
- Pulmonary Arterial Hypertension Symptom Scale (PAHSS)

- Health-related quality of life in pulmonary arterial hypertension (EmPHass-10)
- System Usability Scale – MMPH (SUS)
- Pain Scale, Anxiety, Fatigue, Dyspnea
-

12.4 *Describe any source records that will be used to collect data about subjects (e.g. school records, electronic medical records).*

We will not use an additional source of records to collect data about subjects in this study.

12.5 *Indicate whether or not individual subject results, such as results of investigational diagnostic tests, genetic tests, or incidental findings will be shared with subjects or others (e.g., the subject's primary care physician) and if so, describe how these will be shared.*

NOT APPLICABLE

12.6 *Indicate whether or not study results will be shared with subjects or others, and if so, describe how these will be shared.*

NOT APPLICABLE

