18.0 Provisions to Protect the Privacy Interests of Subjects

18.1 Describe how you will protect subjects' privacy interests during the course of this research.

NOTE: Privacy refers to an individual's right to control access to him or herself. Privacy applies to the person. Confidentiality refers to how data collected about individuals for the research will be protected by the researcher from release. Confidentiality applies to the data.

Examples of appropriate responses include: "participant only meets with a study coordinator in a classroom setting where no one can overhear", or "the participant is reminded that they are free to refuse to answer any questions that they do not feel comfortable answering."

To protect participants' privacy interests and safety during the study, a research team member will only contact the participants on the phone in a private office where no one can overhear the conversation. Any email communications with participants will be kept private and confidential. All data collected during the study will be stored on a secure, password-protected cloud that only the research team has access to.

About Zoom communication, participants will meet with a study coordinator from the privacy of their home where no one can overhear the discussion about their participation in the study. Participants will be reminded not to discuss any personal information outside of the group discussion during the Zoom intervention.

The participant will be reminded that they are free to refuse to answer any questions that they do not feel comfortable answering.

18.2 Indicate how the research team is permitted to access any sources of information about the subjects.

*NOTE: Examples of appropriate responses include: school permission for review of records, consent of the subject, HIPAA waiver. This question **does apply** to records reviews.*

Sources of information about the subjects before enrollment will only be accessible to PH doctors. Once enrolled, research data will be stored in Research Files at UBSON, and only research team members (PI, co-I, RA) will have access. There will be no need for medical record review because the outcome data will be participant-reported outcomes (symptom presence, symptom severity, quality of life).

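### Chi-square is the only method named for categorical outcomes, and it does not test before-after change in symptom presence

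*Combined protocol and SAP*

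**What the plan says.** Hypothesis 2 (section 2.2) states, for long-term impacts: "Participants will report decreases in the prevalence and intensity of PH-related symptoms". Prevalence is therefore named alongside intensity, as a separate thing. Section 12.2 lists "symptom presence and severity" among the data to be collected. Section 18.2 says that "the outcome data will be participant-reported outcomes (symptom presence, symptom severity, quality of life"). Table 1 in section 12.1 schedules the PAHSS in the first, fourth and eighth weeks, so the same people answer three times.

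Section 19.1 then says: "We will compare clinical outcomes within-group (pre-post) as well as between groups in the post-intervention period". The methods it lists are "mixed-effect modeling for repeated measures, and within-group and between-groups comparisons using t-tests or Wilcoxon signed-rank test as appropriate", a paired and an independent t-test, repeated-measures ANOVA and, for categorical data: "For categorical variables and non-normally distributed variables, we will use non-parametric statistical methods (X2"). Neither McNemar's test nor any exact test appears anywhere. The mixed-effect model is listed without an outcome, distribution or link.

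On size, section 5.1 plans for 20 enrolled, "with at least 16 participants to address study aims (8-10 in each Group").

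**The concern.** Whether a symptom is present is a yes/no variable. Its pre-post comparison uses two answers from each person, and the evidence for change lies in the people whose answer switches. Ordinary chi-square does not use that information. It can be set up in two ways, and both fail:

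- **Stacked:** a before/after by present/absent table counts each person twice, as if two independent people had answered.
- **Cross-tabulated:** a before-by-after table of persons tests whether the two answers are associated. They will be, whether or not anything changed.

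The paired methods that 19.1 does name are a t-test and a rank test for scores, so nothing in the list is designed for paired yes/no data. A second, smaller worry is that chi-square relies on a large-sample approximation, while the between-group comparison has 8-10 people per group.

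At stake is the prevalence part of Hypothesis 2. Depending on the table the analyst builds, a symptom that did not change could be reported as significant, or a real fall could be missed.

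**Working it through.** **Inputs from the documents.** 20 enrolled with 20% attrition (5.1): 20 x 0.80 = 16, or 8 per group, which matches the plan's minimum. Section 7.3 gives 15% attrition: 20 x 0.85 = 17, which does not alter the point. Group sizes of 8 to 10 are used below.

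**Assumptions.** The documents give no alpha, symptom prevalence or within-person correlation. I take a two-sided 5% level, prevalence p of 50% or 70%, and phi = 0.5.

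**1. Pre-post, no true change.** With equal prevalence p before and after, the cell probabilities are: present both times = p^2 + phi x p(1-p); each switching cell = p minus that; absent both times = the remainder.

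- p = 0.5: 0.25 + 0.5 x 0.25 = 0.375; switching cells 0.125 each; absent 0.375.
- p = 0.7: 0.49 + 0.5 x 0.21 = 0.595; switching cells 0.105 each; absent 0.195.

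Enumerating every possible table gives these rejection rates at nominal 5%:

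| n | p | Stacked chi-square | Cross-table chi-square | Exact McNemar |
|---|---|---|---|---|
| 8 | 0.5 | 1.3% | 33.3% | 0.01% |
| 8 | 0.7 | 0.8% | 31.2% | 0.005% |
| 10 | 0.5 | 0.5% | 34.3% | 0.06% |
| 10 | 0.7 | 0.5% | 36.8% | 0.02% |

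A large-sample check explains the stacked column. The true variance of the change is 2p(1-p)(1-phi)/n, but stacking assumes 2p(1-p)/n. With phi = 0.5 the effective cut-off is 1.96/sqrt(0.5) = 2.77, so the rejection rate is about 0.6%. A larger sample does not cure this. The cross-table error grows with n: at n = 20 it is about 62% for both prevalences.

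**2. Two illustrations, n = 10.**

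- Five people have the symptom both times and five have it neither time, so nobody changes. The cross-table chi-square is n x phi^2 = 10 x 1 = 10, p = 0.0016.
- Prevalence falls from 9/10 to 4/10, with five losing the symptom and none gaining it. The cross-table chi-square gives p = 0.39.

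The same table flags no change as significant and misses a marked fall.

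**3. Between groups.** The smallest expected count cannot exceed half the smaller group: 4.0 at 8 v 8, 4.5 at 9 v 9, and 5.0 at 10 v 10 (only when exactly half of all participants have the symptom). Enumerating two independent binomials over prevalences of 1-99% gives a maximum true type I error for uncorrected chi-square of:

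- 8 v 8: 7.7%
- 9 v 9: 5.7%
- 8 v 10: 5.3%
- 10 v 10: 4.2%

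**4. What an exact paired test can detect.** Its p-value when all k switches go one way is 2 x 0.5^k. For k = 5 this is 0.0625 and for k = 6 it is 0.031, so at least six switches, all in one direction, are needed for p < 0.05. If prevalence falls from 80% to 40% with phi = 0.4 (both assumed), power is about 5% at n = 8 and 17% at n = 10.

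**The case against.** Four objections deserve weight.

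- **No test is assigned to prevalence by name.** A reader might infer that the plan commits every PAHSS symptom to a chi-square test. It does not. PAHSS scoring is not given, so prevalence could be a per-person count, and the mixed-effect model is listed without an outcome. Section 19.1 also defers to survey-specific recommendations, but supplies none. This stands: the finding rests on the natural reading of the only categorical rule given.
- **Chi-square is not flatly invalid at 8-10 per group.** A reader might infer that it is from the expected-count rule of 5. That rule is a convention. The inflation is material at 8 v 8, slight at 9 v 9 and absent at 10 v 10. Unreliable is the most that can be said.
- **Single p-value contrasts can mislead.** For five switches to none, exact McNemar gives 0.0625, but asymptotic McNemar gives (5-0)^2/5 = 5, p = 0.025, and mid-p gives 0.031. For 7/8 v 3/8, chi-square gives 0.039 and Fisher 0.119, but the exact unconditional tests give 0.053. These gaps mostly show how conservative some exact tests are, not the cost of ignoring pairing, so I do not rely on them.
- **The exact paired test is more conservative still.** In the scenarios above its size is at most 0.06%. This also stands, and it shapes the fix.

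None of these rescues chi-square for pre-post data. A McNemar-type test is conservative but asks the right question; the cross-table asks a different one.

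**Conclusion.** The paired defect holds. The plan pairs pre-post comparisons with a categorical rule that names only chi-square, and ordinary chi-square does not test paired change. Under no change, with prevalence of 50-70% and phi of 0.5 assumed, it rejects 0.5-1.3% of the time stacked and 31-37% cross-tabulated. Other values would move these figures, but any positive within-person correlation pushes them in the same directions. Between groups the approximation is unreliable at the planned minimum, with a worst case of 7.7% at 8 v 8.

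This is a should-fix. A reader might infer that the trial's main conclusions are compromised, but the documents do not support that. It is a 20-person pilot of feasibility, acceptability and preliminary impact, the endpoints in section 3.1 are PAHSS severity and EmPHasis-10, and no decision rule rests on a prevalence p-value. Prevalence is one phrase in Hypothesis 2, although it is a named prediction.

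**What to change.** In section 19.1:

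1. State how prevalence is scored: each participant's number of PAHSS symptoms present at each assessment. Analyse that count with the repeated-measures model already planned.
2. For any single yes/no symptom, use a McNemar-type paired test (exact or mid-p, chosen in advance) pre-post and an exact test between groups. Lead with the estimated change or difference and its exact confidence interval, and present these results as descriptive.
3. Keep chi-square out of all pre-post comparisons. Reword the sentence that also sends non-normal variables to it, since a skewed symptom count would otherwise fall under the same rule despite the Wilcoxon test named earlier in the section.

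The cost is a few sentences and no new data. The downside is that exact tests have very little power at 8-10 per group, so single-symptom results will rarely reach significance. The per-person count and the intervals should carry the message.
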